8.2 SECONDARY OBJECTIVES

The secondary objectives of the study are as follows:

1. To evaluate the change in bladder pain from baseline to 24 hours, using the sum of pain intensity differences (SPID-24) at defined time points, after administration of intravesical URG101 compared with alkalinized Lidocaine Hydrochloride Injection (20 mg/mL) alone, alkalinized Heparin Sodium Injection (5,000 USPU/mL) alone, and placebo [REDACTED]
2. To evaluate the change in urgency from baseline to 12 and 24 hours, using the sum of urgency intensity differences (SUID) at defined time points, after administration of URG101 compared with alkalinized Lidocaine Hydrochloride Injection (20 mg/mL) alone, alkalinized Heparin Sodium Injection (5,000 USPU/mL) alone, and placebo [REDACTED]
3. To evaluate the absolute and percentage change in bladder pain and urgency intensity differences at 1, 12, and 24 hours after administration of URG101 compared with alkalinized Lidocaine Hydrochloride Injection USP (20 mg/mL) alone, alkalinized Heparin Sodium Injection USP (5,000 USPU/mL) alone, and placebo [REDACTED]
4. To evaluate the change in improvement of symptoms using the Patient Global Assessment (question number 3) after treatment with URG101 compared with alkalinized Lidocaine Hydrochloride Injection (20 mg/mL) alone, alkalinized

Heparin Sodium Injection (5,000 USPU/mL) alone, and placebo (███████████) at 1, 12, and 24 hours

5. To evaluate the time to first administration of rescue medication for pain after treatment with URG101 compared to alkalinized Lidocaine Hydrochloride Injection (20 mg/mL) alone, alkalinized Heparin Sodium Injection (5,000 USPU/mL) alone, and placebo (███████████)
6. To investigate the relationship of plasma lidocaine concentrations at 1 hour after study drug administration to bladder pain and urgency at 1 hour, and from baseline to 12 and 24 hours, using the sum of pain and urgency intensity differences at defined time points, after treatment with URG101 compared with alkalinized Lidocaine Hydrochloride Injection USP (20 mg/mL) alone, alkalinized Heparin Sodium Injection USP (5,000 USPU/mL) alone, and placebo (███████████)
7. To evaluate the safety and tolerability of intravesical administration of URG101

9.0 INVESTIGATIONAL PLAN

9.1 OVERALL STUDY DESIGN AND PLAN

This is a phase 2a, prospective, randomized, double-blind, placebo-controlled, multicenter, single-dose, pharmacokinetic study designed to determine the efficacy and safety of the combination product (URG101) versus its alkalinized individual components (Heparin Sodium and Lidocaine Hydrochloride) and placebo [REDACTED]
[REDACTED].

In this study, alkalinized Lidocaine Hydrochloride Injection (20 mg/mL) and alkalinized Heparin Sodium Injection (5,000 USP U/mL) will be subsequently referred to by the drug names alkalinized Lidocaine and alkalinized Heparin.

Eligible subjects exhibiting interstitial cystitis symptoms who have signed informed consent, will be screened and provisionally enrolled for intravesical treatment. Treatment may occur on the day of the Screening Visit (Visit 1) or any following day up to 1 week (Baseline and Drug Administration, Visit 1a). **If drug administration occurs on same day as screening then all assessments in Visit 1 and Visit 1a will be combined.** Confirmation of symptom severity must be obtained before randomization: minimum pain score of 5 on the 11-point numerical rating scale [NRS] at Screening and 15 minutes (\pm 5 minutes) after voiding prior to study drug administration. There is no minimum score requirement for the urgency NRS scales for patients to enter the study. Subjects will become fully enrolled upon receipt of acceptable qualifying laboratory evaluations and clinical assessments obtained before randomization.

On the day of study drug administration (V1a), subjects will be randomized (2:1:2:1; URG101:placebo:lidocaine:heparin) and will receive a single administration of one of four intravesical treatments in a blinded fashion, based on random assignment:

1. URG101 (buffered lidocaine-heparin)
2. Placebo: [REDACTED]
3. Lidocaine alone: [REDACTED]
4. Heparin alone: [REDACTED]

During the study, subjects will be allowed to take their protocol-allowed medications at their usual doses. Additionally, they may use only a short acting non-steroidal anti-inflammatory drugs (NSAIDs) as rescue medication, not sooner than 8 hours after receiving study medication and not within 6 hours prior to receiving study medication ([Table 1](#)).

9.1.1 Screening (Visit 1)

The purpose of the Screening Visit is to obtain informed consent and to establish protocol eligibility. Informed consent will be obtained after the study is fully explained to each subject and before the conduct of any screening procedures or assessments. Procedures to be followed when obtaining informed consent are detailed in [Section 5.1](#).

At the Screening Visit (V1), the following will be completed:

- medical history and demographics;
- medication history;
- the Pelvic Pain and Urgency/Frequency (PUF) questionnaire;
- 11-point NRS for bladder pain and urgency;
- a physical examination, including a pelvic examination (which may be performed without speculum) to confirm lower urinary tract tenderness and vital signs (i.e., systolic and diastolic blood pressure, heart rate, respiratory rate, and oral body temperature); Results from a pelvic examination performed within 7 days prior to the Screening Visit (V1) may replace a V1 pelvic examination.;
- blood and urine samples for safety laboratory assessments (including urine hematuria analysis);
- urine pregnancy test for women of childbearing potential;
- urine screen for drugs of abuse;
- adverse events;
- and concomitant medications.

With the exception of qualifying results for hematuria, drugs of abuse and pregnancy, no other clinical laboratory results are required prior to randomization.

9.1.2 Baseline and Single-Dose Administration (Visit 1a)

Randomization will occur after receipt of adequate qualifying urinalysis test results for drugs of abuse, hematuria and pregnancy and completion of qualifying assessments as documented in [Section 9.3](#). Study drug administration may occur on the day of screening or on any following day up to 1 week after screening, depending on the qualifying day of dosing residual urine assessment and 11-point bladder pain and urgency analog scales, which are administered 15 minutes (\pm 5 minutes) after voiding just prior to administration of study drug.

The following assessments will occur at the site prior to study drug administration ([Table 4](#)):

- urine pregnancy test for women of childbearing potential (must be repeated at V1a if screening [V1] does not occur on the same day as baseline and drug administration [V1a]);
- urine screen for drugs of abuse (must be repeated at V1a if screening [V1] does not occur on the same day as baseline and drug administration [V1a]);
- [REDACTED]
- [REDACTED]
- [REDACTED]
- [REDACTED]
- [REDACTED]
- [REDACTED]
- dispense urination log and symptom diary;
- 11-point NRS for bladder pain and urgency [REDACTED] prior to study drug administration [time 0]);
- vital signs measurements (i.e., systolic and diastolic blood pressure, heart rate, respiratory rate, and oral body temperature). Measurements will be obtained immediately prior to study drug administration (time 0);
- blood sample collection for prothrombin time (INR) and activated partial thromboplastin time (aPTT) prior to the dose at time 0;

- blood sample collection for plasma lidocaine prior to the dose at time 0;
- randomization;
- catheter tolerance assessment;

The following assessments will occur at the site after study drug administration ([Table 4](#)):

- study drug administration via urethral catheter installation (the study medication should left indwelling for 45 minutes [but not less than 30 minutes] before voiding);
- 11-point NRS for bladder pain and urgency 30 minutes (\pm 5 minutes), 1 hour (\pm 5 minutes), 2 hours (\pm 10 minutes) after study drug administration;
- blood sample collection for prothrombin time (INR) and activated partial thromboplastin time (aPTT) at 1 hour (\pm 10 minutes) after study drug administration;
- blood sample collection for plasma lidocaine at 1 hour (\pm 10 minutes) after study drug administration;
- the PORIS questionnaire at 1 hour (\pm 15 minutes) after study drug administration;
- vital signs measurements (i.e., systolic and diastolic blood pressure, heart rate, respiratory rate, and oral body temperature) will be obtained at 1 hour (\pm 15 minutes) after study drug administration;
- concomitant medications;
- and adverse events.

9.1.3 Home Assessment

After instructions, the subjects will be discharged from the clinic and reminded to

return the next day for the optional 24 hour Follow-up Visit. However, return of subject diaries including 24 hour assessments are mandatory. All assessments and their respective timing are provided in Table 4. The following assessments will occur >2 hours post study drug administration but before 24-hour Follow-up Visit (V2):

- 11-point NRS for bladder pain and urgency at 4 hours (\pm 30 minutes), 6 hours (\pm 30 minutes), 8 hours (\pm 30 minutes), 10 hours (\pm 30 minutes), and 12 hours (\pm 30 minutes) (only during times the subject is awake);
- the PORIS questionnaire at 12 hours after study drug administration or before the subject goes to bed for the evening;
- urination log;
- adverse event reporting;
- and concomitant medications.

9.1.4 24-Hour Follow-up Visit (Visit 2; Optional)

Approximately 24 hours after study drug administration, the subjects will return to the clinic for end-of-study assessments. The following assessments will occur:

- subject's diary collection is mandatory to evaluate the efficacy of URG101;
- 11-point NRS for bladder pain and urgency at 24 hours (\pm 2 hours) is mandatory to be completed and returned;
- the PORIS questionnaire at 24 hours (\pm 2 hours) after study drug administration is mandatory to be completed and returned;
- vital signs measurements at 24 hours (\pm 2 hours) after study drug administration (i.e., systolic and diastolic blood pressure, heart rate, respiratory rate, and oral body temperature) is optional;
- and recording of any adverse events or concomitant medications is mandatory to be collected and returned for safety evaluation.

In the opinion of the Investigator, if the subject appears responsible to perform the 24 hour assessments, correctly fill out the diary for all of the at home assessments, and the Investigator and the subject have made acceptable arrangements for the return of the diaries, answering of any follow up questions, and for the subject's treatment and care after 24 hours, then Visit 2 may be considered an optional protocol visit to the clinic.

9.1.5 End-of Study Follow-up

The site staff will call each subject within 48 to 72 hours of study drug administration to check on subject status and to ascertain AE and concomitant medication status.

9.1.6 Interim Study Analysis

After recruitment and treatment of the first ~90 (50%) of the planned 180 subjects, the IDMC will examine the conditional power and determine if a modification to the sample size up to 300 subjects is required to yield an overall power of 90%. An adjustment to the type 1 error rate will not be necessary if the conditional power is >39% at the interim assessment.

The IDMC will consist of 3 members: 1 physician expert in IC/BPS, 1 expert in clinical development, and a biostatistician. None of the IDMC members will be associated with study personnel; all communication between the IDMC and study personnel will be pre-defined and governed by the IDMC charter. The IDMC will have access to unblinded pain scores to perform their assessment of conditional power.

9.2 DISCUSSION OF STUDY DESIGN INCLUDING CHOICE OF CONTROL GROUPS

The URG101 drug product contains the active ingredients, heparin and lidocaine, buffered to a pH of 7.4 (± 0.2). The anesthetic effect of lidocaine is anticipated to provide primary symptom relief of anesthetizing and “down-regulating” the bladder sensory nerves^{13,15,17,20}. Heparin is expected to potentiate this effect by coating the bladder epithelium and reducing the leak of additional potassium that would provoke

the nerves and initiate more symptoms. It is unlikely that heparin alone could provide much in the way of relief since the bladder sensory nerves would still remain “up-regulated” and volume sensitive even though the heparin would reduce the potassium leak. In a clinical trial that evaluated intravesical heparin, there was only minimal benefit, and most of the benefit of chronically administered heparin was after many months of use¹⁸. Therapeutic trials in this population are difficult to conduct due to recruitment issues. It has been shown that it can take more than 3 years to accrue 125 subjects with up to 10 active sites involved⁹.

A practical solution is proposed to evaluate the contribution of the components which is a four-arm study: (1) combination product, URG101, heparin-lidocaine buffered to pH 7.4 (\pm 0.2); (2) placebo [REDACTED] pH 7.4 [\pm 0.2]); (3) lidocaine buffered to pH 7.4 \pm 0.2; and (4) heparin buffered to pH 7.4 (\pm 0.2). Such a study would answer this critical question: Does heparin potentiate the lidocaine effect and justify the combination of the drugs?

Randomization will be used in this study to avoid bias in the assignment of subjects to treatment, to increase the likelihood that known and unknown subject attributes (e.g., demographics and baseline characteristics) are equal across treatment groups, and to ensure the validity of statistical comparisons across treatment groups. Blinding to treatment will be used to reduce potential bias during data collection and evaluation of endpoints.

9.3 SELECTION OF STUDY POPULATION

An estimated 180 subjects will be randomized at approximately 30 sites. A maximum of 300 subjects will be enrolled as determined by the IDMC. Subjects who do not meet all of the inclusion criteria or who meet any of the exclusion criteria will not be eligible to receive study drug.

9.3.1 Inclusion Criteria

Subjects diagnosed with interstitial cystitis/bladder pain syndrome must meet all of the following criteria to participate in the study:

1. Have provided written informed consent to participate in this trial
2. Be male or female, \geq 18 years of age

3. Have moderate-to-severe symptoms of bladder pain of bladder origin for at least 9 months prior to the study
4. May or may not have received a cystoscopy in association with their diagnosis of interstitial cystitis/bladder pain syndrome prior to or at time of screening
5. Have a score of ≥ 15 and < 30 on the PUF questionnaire, completed at screening
6. A minimum score of 5 is required on the 11-point bladder pain NRS
7. Have been using a stable dose of hormone therapy for ≥ 3 months, if female and currently taking hormone therapy (postmenopausal women who have not been stabilized on a regimen of hormone replacement therapy within 3 months of screening will not be included)

9.3.2 Exclusion Criteria

Subjects who meet any of the following criteria will be excluded from participating in the study:

1. For females, have a positive pregnancy test at screening or be pregnant or lactating

Note: Females considered to be of child-bearing potential must commit to using a consistent and medically acceptable method of birth control for the duration of the study: hormonal (i.e., oral, transdermal patch, implant, or injection) on a stable dose for at least 3 months prior to screening; double barrier (i.e., condom with spermicide or diaphragm with spermicide) consistently for at least 2 weeks prior to screening; and intrauterine device for at least 3 months prior to screening; or only have a partner who has been vasectomized for at least 6 months prior to screening or exclusively has same-sex partners. Females considered to be of non-childbearing potential include: at least 1 year postmenopausal; surgically sterile (tubal ligation, bilateral oophorectomy, salpingectomy, or hysterectomy); congenitally sterile; diagnosed as infertile and not undergoing treatment to reverse infertility. If male and sexually active, the patient is willing to commit to an acceptable method of birth control for the duration of the study or exclusively has same-sex partners.

2. Have a known hypersensitivity to heparin or lidocaine

3. Have used any local anesthetic by any route within 24 hours prior to study drug administration, or used a lidocaine patch within 14 days prior to study drug administration
4. Have used a tricyclic antidepressant, or a gamma-Aminobutyric acid (GABA) analogue (gabapentin or pregabalin), unless taking a stable dose of the medication for \geq 3 weeks. The stable dose of gabapentin may not exceed 1,200 mg per day, and the stable dose of pregabalin may not exceed 150 mg per day.
5. Have used any pain medication within 6 hours prior to study drug administration
6. Have used narcotics or medical marijuana \leq 3 weeks prior to study entry (generic names: fentanyl, hydrocodone, hydromorphone, levorphanol, medical marijuana, methadone, morphine, oxycodone, propoxyphene, tramadol). Subjects who have received codeine within this time period may be admitted if the use is not chronic, and not within 6 hours of enrollment, such that they are not at risk for GI or opiate withdrawal symptoms that in the opinion of the investigator would impact the subject's study participation due to their ability to follow the study protocol or bias study results.
7. Have used prohibited drugs as determined by self-report, positive urine drug screen, or in the opinion of the investigator be under the influence of drugs affecting mentation precluding their ability to follow the study protocol or bias study results
8. Have a known clinically significant abnormal laboratory test value defined by the investigator (If a known clinically significant abnormal laboratory value exists, the investigator can request a waiver from the medical monitor. The subject may not continue in the study without an approval waiver from the medical monitor)
9. Have a neurogenic bladder or other disorder that, in the opinion of the investigator, may cause neurogenic bladder (including Parkinson's disease, multiple sclerosis, epilepsy, myasthenia gravis, movement disorders, spinal cord damage)
10. Have pain or a pain disorder that, in the opinion of the investigator, would make it difficult to discriminate pelvic pain of bladder origin from the other pain
11. Have any of the following CNS conditions that in the opinion of the investigator would impact the subject's study participation due to their ability to follow the

study protocol or bias study results, severe diagnosed: major depressive disorder, bipolar disorder, schizophrenia, general anxiety disorder, attention deficit disorder, obsessive compulsive disorder, or other major central nervous system disorder

12. Have history of arrhythmias, conduction disturbances, or cardiac disease, or any coexisting medical condition that, in the opinion of the investigator, may be significant or interfere with study procedures or interpretation of study results
13. Had bladder instillation therapy within 7 days prior to study entry or had a prior bladder instillation with heparin and lidocaine and did not respond
14. Had dilatation (hydrodistention) of bladder within 3 months of study entry
15. Evidence or suspected presence of cancer detected during cystoscopy prior to or at time of initial screening.
16. Has received any investigational drug or device within 30 days prior to screening
17. Is currently enrolled in another investigational drug or device study
18. Is unwilling or unable to abide by the requirements of the study
19. Have an actively bleeding lesion or area in the bladder as detected by dipstick urinalysis and investigator assessment, immediately prior to randomization ([Section 9.5.1.5](#). If the investigator determines that active bleeding is not occurring and that it is safe for the subject, the subject may continue in the study.)
20. Have had any of the following:
 - Bacterial cystitis within 30 days as demonstrated by a positive urine culture ($\geq 10^5$ bacteria per mL)
 - History of pelvic irradiation or radiation cystitis
 - History or presence of uterine, cervical, pelvic, rectal, ovarian or vaginal cancer
 - History of benign or malignant bladder tumors
 - Current chemotherapy
 - History or presence of tuberculous cystitis

- History or presence of chemical cystitis, including that due to cyclophosphamide
- History or presence of urinary schistosomiasis
- Bladder or ureteral calculi
- Clinically significant infectious vaginitis
- Currently uncontrolled genital herpes
- History or presence of urethral diverticulum
- Presence of bladder fistulae
- History of ketamine use

Immediately prior to receiving treatment of study drug, subjects will be re-evaluated as follows: Subjects will be asked to void; 15 minutes (\pm 5 minutes) after voiding, their urinary bladder volume will be measured to rule out diuresis by using an ultrasonic bladder scan or by inserting a catheter and collecting urine. The 11-point bladder pain NRS will also be administered at this time. Subjects will be excluded based on the following criteria:

- Score of < 5 on the 11-point bladder pain NRS (Note: No minimum is needed for urgency NRS.)
- [REDACTED]
- [REDACTED]
- [REDACTED]
- Significant urethral discomfort upon urethral catheterization

9.3.3 Removal of Subjects from Therapy or Assessment

The investigator may withdraw the subject from the study at any time for safety or administrative reasons. The subject may withdraw from the study at any time for any reason.

9.3.3.1 Entire Study or Treatment Arm(s)

If Urgen terminates or suspends the study for safety or unanticipated other reasons,

prompt notification will be given to IRBs, and regulatory authorities in accordance with regulatory requirements.

9.3.3.2 Individual Center

The investigator will notify Urogen promptly if the study is terminated by the investigator or the IRB at the site.

9.3.3.3 Individual Subject

If a subject discontinues from the study prematurely, the reason must be fully evaluated and recorded appropriately in source documents and the CRF. If the subject is being withdrawn because of an AE, that AE should be indicated as the reason for withdrawal.

Any episodes of suicidal ideation or homicidal ideation will result in withdrawal from the study, based on the investigator's discretion.

All subjects have the right to withdraw at any point during treatment without prejudice. The investigator can discontinue a subject's participation in the study at any time if medically necessary. In addition, subjects meeting the following criteria must be withdrawn from the study:

1. Occurrence of any AE, intercurrent illness or abnormality in a laboratory assessment which, in the opinion of the investigator, warrants the subject's permanent withdrawal from the study
2. Treatment with a prohibited concomitant medication other than the use of appropriate medications for the treatment of AEs under direction of the investigator
3. Subject noncompliance, defined as refusal or inability to adhere to the study schedule or procedures per the investigator's discretion
4. At the request of the subject, investigator, Urogen or designee, or regulatory authority
5. Subject becomes pregnant

6. Subject is lost to follow-up

The investigator will notify Urigen promptly when a subject is withdrawn.

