	
Primary Efficacy Determination: The primary efficacy endpoint will be compared between the URG101 and the lidocaine, heparin, and placebo groups using an analysis of covariance model which will include factors for treatment and baseline pain values. Pairwise comparisons of least squares means between URG101 and each of the other treatment arms will be performed. If the p-value associated with these comparisons is < 0.05 in favor of URG101, the primary aim of the trial will be confirmed.
 
Missing data for efficacy values will be imputed by the last observation carried forward method.
 
Secondary Efficacy Determinations: Analyses of secondary endpoints relating to changes in the NRSs for pain and urgency will be performed using analysis of covariance models similar to that used for the primary efficacy endpoint. Nonparametric methodology in exploratory analyses may be used to supplement the parametric analyses.
 
Treatment group comparisons relative to improvement on the PORIS questionnaire, (Question 3), will be made with standard contingency table techniques.
 
Pharmacokinetic Determinations: A comparison of pain and urgency assessments as measured by 11-point NRS to plasma lidocaine concentrations at 1 hour after study drug administration will be made for the PK set.

	
Safety Determinations: All safety analyses will be performed on the safety analysis set.
 
The change in INR and aPTT at baseline and 1 hour will be compared for the various treatment groups using descriptive statistics.
 
Other Determinations: Demographic and disposition data, randomization, drug administration, medical history, prior and concomitant medications, adverse events, clinical laboratory measurements, vital signs, physical examination findings, and all other safety data will be listed by subject and time point. Descriptive statistics will be tabulated for change from baseline in the vital signs. In addition to clinical and laboratory assessments, subject safety will be monitored by recording adverse events and serious adverse events throughout the study. Any pregnancy that occurs during the study will be promptly reported to the sponsor, but will not be considered a serious adverse event. Treatment-emergent adverse events will be summarized by type, frequency, severity, relationship to study drug, and number of subjects per treatment. Adverse events will be coded according to the Medical Dictionary for Regulatory Activities.

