9.7.2 Handling of Missing Data

9.7.2.1 11-Point Bladder Pain and Urgency Scales

For the 11-point numerical data, if subjects are administered any rescue pain medication, the pain score recorded immediately prior to receiving the rescue pain medication will be carried forward for 4 hours. Data for subjects who withdraw will be imputed using the baseline observation carried forward method. The imputed dataset will be used to derive the SPID score.

9.7.2.2 24-Hour Symptom and Urination Diaries

During the 24 hours after treatment, subjects are required to fill in their symptom diaries only while they are awake. Missing data occurring will be imputed using LOCF methodology.

[figure not shown]
If the number of missing data points in the 12-hour period after treatment administration is 6 or greater, then the subject is considered a major protocol violator and his or her data are excluded from the per protocol analysis. If the number of missing data points in the first 6-hour period following treatment administration is 3 or greater, then the subject is considered a major protocol violator and the subject's data are excluded from the per protocol analysis.

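### Withdrawing a dosed subject from the study for a prohibited medication can end collection of home pain scores for SPID-12, and the visible rules for filling the gap conflict

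*Combined protocol and SAP*

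**What the plan says.** Section 9.3.3.3 states that "subjects meeting the following criteria must be withdrawn from the study", and its second criterion is "Treatment with a prohibited concomitant medication other than the use of appropriate medications for the treatment of AEs under direction of the investigator". Each subject receives a single dose (9.4.5). The ITT set is every randomized subject who receives study drug (9.7.1.5), and it carries the primary analysis (9.7.1.14).

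Pain is scored in clinic at 0.5, 1 and 2 h (9.1.2) and at home at 4, 6, 8, 10 and 12 h (9.1.3). Section 9.5.7 asks subjects who discontinue for Visit 2 procedures and the follow-up call where possible. Visit 2 (9.1.4) covers return of the diary and the 24 h items. Neither section asks for the home scores to continue.

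The visible text has these rules for gaps and rescue:

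- Section 9.7.2.1, rescue: "if subjects are administered any rescue pain medication, the pain score recorded immediately prior to receiving the rescue pain medication" is carried forward for 4 hours.
- Section 9.7.2.1, withdrawal: "Data for subjects who withdraw will be imputed using the baseline observation carried forward method".
- Section 9.7.2.2, diaries: "Missing data occurring will be imputed using LOCF methodology".
- Synopsis, primary efficacy determination: "Missing data for efficacy values will be imputed by the last observation carried forward method".

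After dosing, section 9.1 permits only short-acting NSAIDs as rescue, and not before 8 h.

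**The concern.** Once the only dose is in, removing a subject from the study protects nobody from further exposure. It only stops measurement in someone who will be analysed anyway. A subject in enough pain to take a non-permitted analgesic at home may therefore lose later primary-endpoint scores that could still have been collected.

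What fills the gap is not settled either. Section 9.7.2.1 says BOCF for a withdrawn subject, and the synopsis says LOCF for missing efficacy values without exception. If the medication was an analgesic taken for bladder pain, the 4-hour rescue rule can apply to the same subject. These rules credit different amounts of relief to the same record.

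**Working it through.** **Plan's own figure.** The synopsis claims 90% power for 60 vs 60 at effect size 0.60, and for 60 vs 30 at 0.75. With power = Φ(d/√(1/n₁+1/n₂) − 1.96):

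- 0.60/√(1/60+1/60) = 3.286, giving Φ(1.326) = 90.8%.
- 0.75/√(1/60+1/30) = 3.354, giving Φ(1.394) = 91.8%.

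The figure reproduces, and this point does not challenge it.

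**SPID-12 weights.** The trapezoidal rule on nominal times 0, 0.5, 1, 2, 4, 6, 8, 10, 12 h gives weights 0.25, 0.5, 0.75, 1.5, 2, 2, 2, 2, 1, which sum to 12.

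**Weight on scores still to come when the analgesic is taken.** The 4-hour rule replaces scores inside its window, so where it governs, only scores after the window are lost information.

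| Use at | All later scores | Replaced by 4-hour rule | Left after the window |
|---|---|---|---|
| 3 h | 9/12 = 75% | 4, 6 h | 5/12 = 42% |
| 5 h | 7/12 = 58% | 6, 8 h | 3/12 = 25% |
| 7 h | 5/12 = 42% | 8, 10 h | 1/12 = 8% |

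**One subject (invented).** Baseline is 7. Scores are 4, 4, 4, 5 at 0.5, 1, 2, 4 h, with an NSAID at 5 h. Had scoring continued, the scores at 6 to 12 h would be 3, 3, 4, 4. The part up to 4 h contributes 0.5×3 + 0.75×3 + 1.5×3 + 2×2 = 12.25.

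| Handling of 6, 8, 10, 12 h | Differences from baseline | SPID-12 |
|---|---|---|
| BOCF | 0, 0, 0, 0 | 12.25 |
| 4-hour rule, then BOCF | 2, 2, 0, 0 | 12.25 + 8 = 20.25 |
| LOCF | 2, 2, 2, 2 | 12.25 + 14 = 26.25 |
| 4-hour rule, then observed | 2, 2, 3, 3 | 12.25 + 17 = 29.25 |
| As observed | 4, 4, 3, 3 | 12.25 + 25 = 37.25 |

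The first three need no score after 5 h. The last two are possible only if scoring continues.

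**Trial level.** The documents give no rate of such use and no SD, so the effect cannot be computed. As a rough guide, a simulation with every input assumed used:

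- 4000 runs, 60 per arm, baseline 5 to 9;
- mean pain difference 2.68 vs 1.5, between-subject SD 1.9, within-subject SD 1.2;
- analgesic at a uniform time from 2 to 8 h, more likely with less relief, giving 2 points of relief for 6 h;
- a two-sided t test.

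Without analgesic use it gives a difference of 13.0, or 0.60 SD, with 90% power. Mean difference (power) by share using an analgesic:

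| URG101 / comparator | BOCF | LOCF | 4-hour rule |
|---|---|---|---|
| 10% / 10% | 12.29 (88.4%) | 13.01 (90.0%) | 13.01 (90.6%) |
| 5% / 10% | 12.58 (89.6%) | 13.04 (90.2%) | 12.87 (89.6%) |
| 5% / 20% | 12.72 (91.0%) | 13.02 (89.6%) | 12.53 (88.0%) |

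The spread among rules is 0.46 to 0.72 points. Divided by the implied SD of 21.6, that is 0.02 to 0.03 SD.

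**The case against.** Much of the case on the other side stands.

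- **Order of rules.** Section 9.7 defers detail to a separate SAP that is not in the text reviewed. A figure in 9.7.2.2 and the body of Table 4 are also not shown. Any of these may settle the order, so its absence from the plan cannot be asserted. The section 9.7.2 rules also have mostly separate triggers. What remains visible is the overlap between rescue and withdrawal, and the synopsis saying LOCF where 9.7.2.1 says BOCF.
- **How much is lost.** Collection stops early only if the site learns of the use before 12 h and acts on it. Entries already in the diary can be recovered, since its return is a Visit 2 procedure. A reader might take the 75%, 58% and 42% column as the information at risk. Where the 4-hour rule applies, the plan would set part of that aside anyway, and the last column is the right one.
- **Meaning of prohibited after dosing.** Table 1 is introduced as restrictions before study drug. That an NSAID before 8 h triggers withdrawal is inferred from section 9.1, and it could be read as a timing breach in a permitted class.
- **Per-protocol set.** A reader might infer that the per-protocol thresholds ("If the number of missing data points in the 12-hour period after treatment administration is 6 or greater"; "If the number of missing data points in the first 6-hour period following treatment administration is 3 or greater") would miss these subjects. Leaving after 2 h gives 5 and 2 missing pain scores, below 6 and 3. If urgency scores also count as data points, the numbers are 10 and 4, and the subject is excluded. The text does not say which, and section 9.7.1.5 leaves other criteria open, so the inference is not supported.
- **Whole-record BOCF.** A reader might suppose that BOCF replaces every score of a withdrawn subject, giving SPID-12 of 0. If that happened to 5%, 10% or 20% of both arms with the SD unchanged, power for 60 vs 60 would be Φ(3.286(1 − w) − 1.96) = 87.7%, 84.1% or 74.8%. BOCF sits under missing-data handling and is more naturally read as filling missing scores, so these figures do not describe the plan.

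**Conclusion.** The concern holds in a limited form. The withdrawal rule has no treatment to stop and can end collection of primary-endpoint scores in subjects who remain in the ITT analysis. The synopsis and section 9.7.2.1 visibly disagree on how a withdrawn subject's gaps are filled, and the rescue and withdrawal rules can both apply to one subject without a visible order.

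For a single subject the choice matters: 12.25 to 26.25 in the invented example when later scores are absent. For the trial it probably does not matter much, at 0.02 to 0.03 SD among the rules in the simulation. That rests wholly on assumed inputs, leaves the form of the link between relief and analgesic use unspecified, and uses a t test in place of the planned ANCOVA. A reader might infer a threat to the primary result, but the documents give neither a frequency nor an imbalance between arms to support one. This is a cheap improvement, held with medium confidence.

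**What to change.** 1. Amend 9.3.3.3 so that a dosed subject who takes a non-permitted medication is recorded as a protocol deviation and considered for per-protocol exclusion, but stays in follow-up and completes all scheduled NRS scores to 24 h, unless the subject chooses to stop or safety requires it. State which medications count as non-permitted after dosing.
2. Apply BOCF only to scores missing after a subject stops providing data.
3. Align the synopsis with 9.7.2.1.
4. Name one primary rule for scores after a non-permitted analgesic and its order relative to LOCF and BOCF, with the alternative as a sensitivity analysis. The 4-hour window should not pass automatically to opioids or long-acting analgesics, since section 9.1 defines rescue as short-acting NSAIDs.

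The fourth step is needed even when scores are kept. In the simulation at 5% / 20%, using every score as observed, which is not a rule in the plan, gave a difference of 11.34 with 83.1% power.

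The cost is one written amendment approved by investigators, IRBs and the sponsor (10.1) at up to 30 sites, and one sensitivity analysis. No new procedure is needed: the diary is dispensed at Visit 1a (9.1.2) and reminder calls are planned (9.5.2.3). The SAP alone could settle the imputation order, but it cannot recover scores never collected.
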